## **Monitoring**

A DSMB will provide independent monitoring of this pilot study in accordance with the BLOODSAFE DSMB charter. The DSMB will have an opportunity to review the protocol

and informed consent and provide feedback prior to study initiation. An open and closed report will be prepared by a DCC statisticians. Interim data summaries will be reviewed at regular intervals by the DSMB (at least twice a year). The DSMB will review adverse event data, other safety data, quality and completeness of study data, and enrolment data at each meeting to ensure proper trial conduct. Study personnel should provide any new literature pertinent to the trial, along with their recommendation as to whether it affects the trial conduct or design. The DSMB will review the consent periodically and/or as needed and consider whether the consent form requires revision in light of any new findings or amendments. In addition to regular meetings, it may be necessary to convene the DSMB urgently on an *ad hoc* basis to discuss new data or other information that raises questions about equipoise, safety, or other issues identified by DSMB members.

## 2 Study Methods

### 2.1 Design

This pilot study has 3 components: 1) a cross-sectional assessment designed to estimate the prevalence of anaemia leading to donor deferral, 2) a cross-sectional assessment designed to estimate the prevalence of ID and IDA among first-time donors, and 3) a longitudinal 2-arm parallel groups trial among first-time voluntary donors that compares haemoglobin levels at 4 months among those who receive iron supplementation to those who do not receive iron supplementation.

### 2.2 Randomization

There is no randomization in the cross-sectional component. In the parallel groups' component, the 2 groups will be determined based on the need for iron supplementation, so the treatment is not assigned by randomization.

### 2.3 Blinding

The participants and the investigators are not blinded.

### 2.4 Sample size

**Cross-sectional study:** Since all potential donors will contribute to the estimate of the proportion of potential donors who are deferred due to low haemoglobin, the estimate of this proportion will be sufficiently accurate to allow for comparisons against yearly rates. As stated above, the annual proportion of deferrals from 2015-2018 ranged from 33-53%. If we assume that 5 blood donors attempt to donate each business day, then there should be about 600 donation attempts over the 6-month enrolment period. Table 1 shows values for the prevalence of low haemoglobin, the corresponding margin of error and the corresponding 95% confidence interval. For example, if the prevalence of low haemoglobin leading to deferral is 50% then a 95% confidence interval would be (46%, 53%) which allows for determination of the prevalence in a range that is smaller than the range of yearly estimates. Note: these estimates were obtained using the usual normal approximation to the sampling distribution of a proportion without a continuity correction.

**Table 1: Precision of prevalence estimates for low haemoglobin leading to deferral.**

Prevalence	Error Margin	95% Confidence Interval
0.2	0.032	0.17, 0.23
0.3	0.037	0.26, 0.34
0.4	0.039	0.36, 0.44
0.5	0.040	0.46, 0.54
0.6	0.039	0.56, 0.64

Since not all participants will consent to participate in the study and only a subset of donors are first-time donors, the precision of estimates of the prevalence of ID and IDA will be lower. Based on the unpublished estimates of the prevalence of ID and IDA provided above (i.e., 63.9% of those with anaemia had IDA and 86.1% of those with anaemia had ID, so 30.7% of the total had IDA and 41.3% had ID), estimates of the prevalence of these conditions cover almost the same range as our estimates of the prevalence of low haemoglobin. Since enrolment for this component of the study entails enrolment in the longitudinal study, the sample size was determined by the requirements for the longitudinal study which is 292 participants. Since some participants in the cross-sectional study of ID and IDA may be found to have haemoglobin (Hb)<10g/dl and will therefore be excluded from the longitudinal study, the sample size for the cross-sectional study may exceed 292. This will require that, on average, almost 2.5 participants per day consent to the study to get to about 300 over the 6-month enrolment period. Table 2 shows values for the prevalence of ID/IDA within deferral strata, the corresponding margin of error and the corresponding 95% confidence interval. For example, if the prevalence of IDA is 30% within one of the strata then a 95% confidence interval would be (25%, 35%) which has a total width comparable to the confidence intervals obtained using all potential donors. The intervals for the post-stratified estimates will be slightly larger due to the sampling variability of the estimated post-stratification weights.

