## Sample size

**Qualitative study:** In all, ten focus groups of 8-10 participants purposively selected with one group from each of the following blood donation categories: (i) religious organizations, (ii) educational institutions, (iii) corporate institutions, (iv) organized community groups, and (v) walk-in blood donors. The aim of the focus groups is to identify barriers and recommendations for using iron supplementation and nutritional counselling to increase the blood donor pool. These discussions may involve gender-sensitive topics and gender may impact participation in the discussion, so two groups of each blood donation category by gender will be formed (e.g., 8-10 females, 8-10 males). The female and male focus groups will meet in separate spaces so only one gender will be interviewed at a time. Thus, there is one male and one female group for each donation category.

**Quantitative method:** Cross-sectional study to determine the prevalence of anaemia among prospective blood donors: There are 2 distinct components of the cross-sectional study: estimation of the proportion of potential donors deferred due to low haemoglobin and the proportion of first-time potential donors who have ID and IDA. The determination of deferral due to low haemoglobin is routinely collected by the National Blood Service Ghana (NBSG) and does not require consent of potential donors in this study. The proportion deferred will be determined using the same donation sites as the other components of the study with an estimated sample size of 600 and resulting margin of error less than 0.04. Consequently, the 95% confidence intervals for deferral prevalence will have a total width of less than 0.08 giving a more precise estimate than the year-to-year variation in the total percentage deferred. Participant consent is needed to draw blood for determination of ID and IDA. We anticipate that 292 participants will consent and be enrolled with resulting margin of error less than 0.057 and total confidence interval width of less than 0.11 for likely values of the prevalence of ID and IDA among first-time potential donors (conditional on deferral status). Thus, the ID and IDA prevalence estimates will have comparable precision to the estimated proportion of those deferred using all potential donors at recruitment sites.

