## **Stratification and Sampling**

The SZBC contributes to the blood service needs of the Western, Central, Greater Accra, Eastern and the Volta Regions of Ghana. In 2018 and 2019, the SZBC attended to an average of 550 prospective voluntary blood donors a week, including 80 walk-in donors. Out of this number, the study will recruit all participants (who fall within the inclusion criteria) reporting per day for up to 6 months until the sample size is attained. Eligible participants will form the sampling frame for the study.

Donors will be informed about the trial and the prevalence study of ID and IDA. Due to a need to recruit approximately equal numbers of participants in the 2 groups in the trial, donors who fail the copper sulphate test will be disproportionately approached for participation. This creates a stratification of donors by status with regard to the outcome of the copper sulphate test. Within these strata the proportion of donors who are ID and IDA will be determined. The estimates of these proportions within strata will be unbiased but if one simply averages over the strata, we expect that the estimates of the proportion who are ID or IDA will have positive bias. However, since we will have estimates of the proportion of donors who fail the copper sulphate test, we can post-stratify the proportions of donors who are ID or IDA by the proportion of donors who fail the copper sulphate test.

Out of the sampling frame, participants will be purposively sampled for FGDs. In all there will be ten FGDs i.e., two groups (male-only and female-only) selected to represent each of the five NBSG voluntary blood donation categories (excluding mass/media event donors), and with each group composed of both first-time and repeat donors. In-depth interviews will also be conducted with blood donation staff and medical officers responsible for blood donation.

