**Table 2: Precision of prevalence estimates for ID and IDA.**

Prevalence	Error Margin	95% Confidence Interval
0.2	0.046	0.15, 0.25
0.3	0.053	0.25, 0.35
0.4	0.056	0.34, 0.46
0.5	0.057	0.44, 0.56

**Parallel groups study:** The primary outcome for this portion of the study is haemoglobin levels at 4 months. Formally the null hypothesis for this outcome is inferiority of treatment of low haemoglobin with iron supplementation among those with

low haemoglobin at screening to no treatment among those without low haemoglobin at screening. The non-inferiority margin is fixed at a value of 1.0 g/dL. Based on recent work in West Africa, the DCC has access to haemoglobin measurements from 1548 individuals between the ages of 17 and 60 who weigh at least 50 kg. Among these individuals the standard deviation of haemoglobin was 1.89 g/dL (the mean was 13.4 g/dL). These individuals did not pass the strict screening criteria used by the NBSG, so this estimate might be slightly inflated and so our power calculations may be somewhat conservative. We specify an alpha level of 0.025 and require power of at least 85%. With these values we can determine the number of participants per arm if we assume a value for the true difference between the groups (the absolute value of this difference must be less than our margin and will generally be negative when the margin is positive to be consistent with the lack of superiority of iron supplementation). Table 3 presents the number of participants per arm under these assumptions for a selection of values for the true difference. We assume that the true difference is -0.3 g/dL and obtain a sample size of 131 participants per arm. If the true difference is larger than -0.3 g/dL (e.g., if there is no difference) then the power will exceed 85%. To allow for loss to follow-up and some participants requiring iron supplementation due to incident anaemia, ID or IDA the sample size has been increased to 292.

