### 3.4 Baseline characteristics

Baseline characteristics for those who enrol in the trial will come from information collected on the screening and enrolment forms. The only characteristics captured for those in the anaemia deferment study are age, sex, if the person has previously donated, and the type of donation (i.e., replacement/family or voluntary). For those in the study of ID/IDA information on abnormal peripheral blood film, malaria, haemoglobin, ferritin, and TTI status will also be obtained. Additional information will be available for those in the trial. For the open report, baseline characteristics will be summarized pooled across the two treatment groups and presented separately for those in the anaemia deferment study, the ID/IDA study, and the trial. Note that these study populations are related as follows: everyone in the trial is in the ID/IDA study, and everyone in the ID/IDA study is in the anaemia deferment study. Note that someone who consents to the trial but is found to have levels of haemoglobin that are too low at screening will participate in the ID/IDA study but will not participate in the trial.

For the closed report, baseline characteristics will be summarized by treatment group for the Iron Supplementation Trial.

The following baseline characteristics will be summarized with counts and percentages for binary and categorical variables, medians and quartiles for continuous variables and ordinal variables when available for each of the 3 components of the study.

Demographics:

- Age: summary as continuous variable.
- Sex.
- First-time donation status (Yes or No).
- Number of children (an integer equal or above 0).
- Marital status (6 options).
- Home situation (6 options).
- Main method of travel (private or public).
- Highest level of education completed (7 options).
- Employment category (8 options).
- Number of expensive, durable consumer items (an integer in the range 0-7).
- Ethnic background (6 options).
- Religion (5 options).

Screening laboratory results:

- Haemoglobin concentration.
- Plasma ferritin concentration.

- Malaria test results from a malaria rapid diagnostic test.
- Abnormal peripheral blood film results reported by type of abnormality (i.e., helminthic infection, malaria, neutrophilia, leucocytosis, and lymphocytosis).
- ID present
- IDA present.

Medical History:

- Diagnoses (19 options, select all that apply).

Nutritional History:

- Number of meals yesterday (4 options).

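### SAP Table 2 is presented as ID/IDA precision within each deferral stratum, but its margins use all 292 participants; at the planned total the smaller stratum's interval is at least about 28% too narrow

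*SAP*

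**What the plan says.** The SAP describes a sample that over-represents donors who fail the copper sulphate test. Of this it says, under Stratification and Sampling in section 1.2: "This creates a stratification of donors by status with regard to the outcome of the copper sulphate test". There are two strata, pass and fail.

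Section 2.4 then introduces Table 2 as showing precision inside those strata, with margins of 0.046, 0.053, 0.056 and 0.057 at prevalences of 0.2, 0.3, 0.4 and 0.5. Its example is "if the prevalence of IDA is 30% within one of the strata then a 95% confidence interval would be (25%, 35", followed by the remark "which has a total width comparable to the confidence intervals obtained using all potential donors". The caption itself, "Table 2: Precision of prevalence estimates for ID and IDA", does not mention strata.

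The sample size text in section 1.2 makes the same claim. It puts the expected number and its precision in these terms: "292 participants will consent and be enrolled with resulting margin of error less than 0.057 and total confidence interval width of less than 0.11". The quantity to which it attaches this precision is described there as "prevalence of ID and IDA among first-time potential donors (conditional on deferral status".

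On the size of the sample, section 2.4 takes 292 from the longitudinal trial. It notes that the cross-sectional number may be larger and plans that "on average, almost 2.5 participants per day consent to the study to get to about 300 over the 6-month enrolment period". Section 3.4 confirms one reason for a larger number: a person whose screening haemoglobin is too low for the trial "will participate in the ID/IDA study but will not participate in the trial". No stratum sizes are given.

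The protocol's Sample size justification has the same Table 2 figures and the same 30% example, without reference to strata.

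**The concern.** A margin that applies to one stratum has to be calculated with the number of people in that stratum. The SAP attaches the margin for the whole sample to each of two strata that share that sample. Two strata cannot each contain 292 of about 300 people.

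The stratum proportions matter because section 7.1 builds the overall ID and IDA estimates from them, and estimating those prevalences is a listed secondary objective. A reader of section 2.4 would expect more stratum-level precision than the planned sample can give. The stakes are limited: what is misstated is planned precision, not an analysis.

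**Working it through.** **Inputs.** Two-sided 95% intervals (SAP 2.5), so z = 1.96. Normal approximation without continuity correction (the note on Table 1 in SAP 2.4, which I take to cover Table 2). Total of 292, or about 300 (SAP 2.4). Two strata (SAP 1.2). The split between strata is not stated.

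**Formula.** Margin = 1.96 × √(p(1−p)/n).

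**Step 1: reproduce the plan's figures.** With n = 600 at p = 0.2 to 0.6 the formula gives 0.032, 0.037, 0.039, 0.040 and 0.039, which is Table 1. For Table 2:

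| Prevalence | SAP Table 2 | n = 292 | n = 300 | n = 150 | n = 146 |
|---|---|---|---|---|---|
| 0.2 | 0.046 | 0.0459 | 0.0453 | 0.0640 | 0.0649 |
| 0.3 | 0.053 | 0.0526 | 0.0519 | 0.0733 | 0.0743 |
| 0.4 | 0.056 | 0.0562 | 0.0554 | 0.0784 | 0.0795 |
| 0.5 | 0.057 | 0.0573 | 0.0566 | 0.0800 | 0.0811 |

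Only n = 292 matches all four rows. Table 2 is therefore a whole-sample table.

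**Step 2: bound the smaller stratum.** Whatever the split, the smaller of two strata holds at most half: 292/2 = 146 or 300/2 = 150. The last two columns are therefore its smallest possible margins at those totals. At 30% prevalence the interval is at best 0.227 to 0.373 (n = 150) or 0.226 to 0.374 (n = 146), against 0.25 to 0.35.

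**Step 3: size of the shortfall.** The stated width divided by the correct width is √(n/292), at any prevalence.
- n = 150: 1 − √(150/292) = 28.3% too narrow.
- n = 146: 1 − √(146/292) = 29.3% too narrow.

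With the printed, rounded 0.053 in place of 0.0526, n = 150 gives 1 − 0.053/0.0733 = 27.7%, which still rounds to 28%.

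**Step 4: the linked statements.** For n = 150 the total widths at the four prevalences are 0.128, 0.147, 0.157 and 0.160, against the stated bound of 0.11. At 30% the width is 0.147, and Table 1 gives 0.073 at the same prevalence, so the ratio is √(600/150) = 2.0. For the whole sample the ratio is √(600/292) = 1.43.

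**Step 5: an unequal split, as illustration.** Assume 30:70 of 292, that is, 88 and 204. At 30% prevalence the margins are 0.096 and 0.063. The stated interval is then 1 − √(88/292) = 45% too narrow for the smaller stratum and 1 − √(204/292) = 16% too narrow for the larger.

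**Step 6: what Table 2's precision would need.** For both strata to reach it, the total would have to be at least 2 × 292 = 584.

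**The case against.** **The total is not capped.** Several trial exclusions (transfusion-transmissible infection, malaria or helminths, haemoglobin below 10 g/dL) do not apply to the ID/IDA study. Losses between screening and enrolment may also leave people with usable screening ferritin. A larger total would shrink the shortfall: at an equal split and assumed totals of 320, 350 and 400 it is 1 − √(160/292) = 26%, 1 − √(175/292) = 23% and 1 − √(200/292) = 17%. So the 28% is tied to the planned 292 to 300. But about 300 is the only larger planning figure the SAP gives, and even 400 leaves a shortfall.

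**The stratum figure is an intermediate step.** The objective is overall prevalence, reached by post-stratification, and the printed margins can be about right for that. The approximate variance is π²p₁(1−p₁)/n₁ + (1−π)²p₀(1−p₀)/n₀ + (p₁−p₀)²π(1−π)/M. Here π is the deferral rate estimated from M donors, and subscripts 1 and 0 mark the deferred and non-deferred strata. All inputs below are assumptions.
- π = 0.35, p₁ = 0.5, p₀ = 0.3, n₁ = n₀ = 146, M = 600: overall prevalence 0.37 and margin 0.0566. The Table 2 formula gives 0.0554, a ratio of 1.02.
- π = 0.2, the same prevalences and M, n₁ = 204, n₀ = 88: overall prevalence 0.34 and margin 0.0781 against 0.0543, a ratio of 1.44.

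This supports reading the fault as mainly one of labelling. It does not make the within-stratum statement true, and it shows that the overall margin also depends on the split. The SAP's remark that post-stratified intervals will be slightly larger because the weights are estimated does not address the number of people in each stratum.

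**Comparable is a loose word.** That stands. Whether a ratio of 2.0 is comparable is a judgement; the margins themselves are not.

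**Conclusion.** The concern holds. Table 2, its 30% example and the matching sentence in section 1.2 state a within-stratum precision that the planned sample cannot give to both strata. At a total of 292 to 300, the smaller stratum's stated interval is too narrow by at least about 28% to 29%. That minimum needs no assumption about the split; it rests only on the planned total, two strata and the SAP's own formula. The 30:70 figures rest on an assumed split.

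The importance is low. No hypothesis test, enrolment target or final interval uses Table 2: the ID/IDA sample size comes from the longitudinal trial, and the final intervals come from posterior draws (SAP 7.1).

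**What to change.** Do one of the following in SAP 2.4:

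1. Relabel Table 2 and its 30% example as the precision of an overall estimate from a simple random sample of 292, and remove the reference to strata.
2. State the expected stratum sizes and recompute the table over a range of splits, for example 30:70, 50:50 and 70:30.

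In either case, correct the sample size text in section 1.2 (the phrase on conditioning by deferral status and the 0.057 and 0.11 figures) and the statements in both sections that the precision is comparable with Table 1. The 0.11 bound needs attention even for the whole sample: at the SAP's own 41.3% ID figure the width is 2 × 1.96 × √(0.413 × 0.587/292) = 0.113. If a post-stratified overall margin is added, show it over a range of deferral rates and stratum prevalences.

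The change affects one table and a few sentences. The analysis method, the number enrolled and the trial sample size stay as they are. The only cost is a less favourable stated precision. The SAP allows updates before database lock.

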**Table 2: Precision of prevalence estimates for ID and IDA.**

Prevalence	Error Margin	95% Confidence Interval
0.2	0.046	0.15, 0.25
0.3	0.053	0.25, 0.35
0.4	0.056	0.34, 0.46
0.5	0.057	0.44, 0.56

**Parallel groups study:** The primary outcome for this portion of the study is haemoglobin levels at 4 months. Formally the null hypothesis for this outcome is inferiority of treatment of low haemoglobin with iron supplementation among those with

low haemoglobin at screening to no treatment among those without low haemoglobin at screening. The non-inferiority margin is fixed at a value of 1.0 g/dL. Based on recent work in West Africa, the DCC has access to haemoglobin measurements from 1548 individuals between the ages of 17 and 60 who weigh at least 50 kg. Among these individuals the standard deviation of haemoglobin was 1.89 g/dL (the mean was 13.4 g/dL). These individuals did not pass the strict screening criteria used by the NBSG, so this estimate might be slightly inflated and so our power calculations may be somewhat conservative. We specify an alpha level of 0.025 and require power of at least 85%. With these values we can determine the number of participants per arm if we assume a value for the true difference between the groups (the absolute value of this difference must be less than our margin and will generally be negative when the margin is positive to be consistent with the lack of superiority of iron supplementation). Table 3 presents the number of participants per arm under these assumptions for a selection of values for the true difference. We assume that the true difference is -0.3 g/dL and obtain a sample size of 131 participants per arm. If the true difference is larger than -0.3 g/dL (e.g., if there is no difference) then the power will exceed 85%. To allow for loss to follow-up and some participants requiring iron supplementation due to incident anaemia, ID or IDA the sample size has been increased to 292.

